**NCT02851992**

TITLE	A prospective study to evaluate long-term clinical outcomes of the Global Tissue Sparing GTS® cementless femoral stem
AIMS	The objective of this prospective clinical study is to obtain multi-center, long-term (10-year) clinical data on the new GTS® femoral stem in its standard and lateralized versions as part of Post Market Surveillance requirements
DESIGN	This is a multicenter, non-controlled, prospective study. 250 subjects (GTS standard and lateralized) will be recruited. Study will be conducted in 5 centers across Europe (Germany, Italy, Spain, France)
OUTCOME MEASURES	
Primary Outcome Measure for all study patients
 
 
Mean Harris Hip Score (HHS) at 2 year postoperative
 
 
Secondary Outcome Measures for all study patients
 
 
Radiographic Evaluation: stability, incidence of radiolucencies around the prosthesis and bone remodeling
 
Patient satisfaction: EQ5D quality of life
 
Adverse Events/Complications (including revisions/removals).
 
Survivorship
 

POPULATION	250 subjects suitable for GTS femoral stem (standard and lateralized) can be included
ELIGIBILITY	
Inclusion criteria
 
Patients inclusion criteria for this evaluation are be in accordance with the indications of the GTS® stem and specifically
 
 
Primary osteoarthritis or secondary coxarthritis
 
Inflammation of the hip: rheumatoid arthritis, etc.
 
Femoral neck fracture
 
Avascular necroses of the femoral head
 
Sequelae from previous operations on the hip, osteotomies, etc.
 
Congenital hip dysplasia
 
 
Additional inclusion criteria include:
 
 
18 years of age or older
 
Subjects willing to return for follow-up evaluations
 
Subjects who read, understood study information and provided an informed written consent (specific local regulatory requirements)
 
 
Exclusion criteria
 
Exclusion criteria are in accordance with absolute and relative contraindications for use for GTS® stem
 
Absolute contraindications include:
 
 
Local or systemic infections.
 
Severe muscular, neurological or vascular deficiencies of the extremity involved
 
Bone destruction or poor bone quality that is likely to affect implant stability (Paget's disease, osteoporosis, etc.)
 
Concomitant disease likely to affect implant function
 
Allergy to any of the components of the implant
 
Patients weighing more than 110 kg
 
 
Additional exclusion criteria:
 
 
Subjects unable to co-operate with and complete the study
 
Dementia and/or inability to understand and follow instructions
 
Neurological conditions affecting movement
 
Patient over 18 under law supervision
 

DURATION	The initial study assessment period will be 12 years; 24 months recruitment and the follow-up clinical reviews for all patients will be at 3 months, 1 year, 2 years, 3 years, 5 years, 7 years and 10 years.
-----------------	---

## 1. STATISTICAL ANALYSIS PLAN

Data will be recorded in a case report form on the basis of one CRF per patient. For bilateral procedures, one CRF per joint must be completed.

Statistical analysis will be performed on an intent-to-treat basis, using for all data the SPSS software (SPSS, Chicago, Illinois). For qualitative variables, the chi-square test and a Fisher test will be performed to detect differences between preoperative and postoperative values. The Student t test will be employed for quantitative variables for comparison between groups.

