### 1.1. SAMPLE SIZE CALCULATION

Patient population was determined based on mean Harris Hip Score (HHS) at 2 years follow-up.

Sample size calculation was led as follows:

$$N = \frac{4 \times \text{STD}^2 \times (Z)^2}{(X - Y)^2}$$

Where:

STD = Standard Deviation

X-Y = Margin of Error or Precision

Z = Z1- $\alpha/2$

In order to determine Harris Hip Score with 95% confidence: then Z = 1.96

If HHS is between 95 to 100: then X=100 and Y=95

Estimate standard deviation of HHS at follow-up = 13

This value has been based on results from previous studies (Reference 1)

$$N = \frac{4 \times (13)^2 \times (1.96)^2}{(100 - 95)^2}$$

N = 104

With attrition rate of 15%

Starting population = N/0.85 = 104/0.85 = 122 rounds to 125 subjects in GTS standard group.

The same calculation applied to GTS varized group.

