### 1.3. HANDLING OF MISSING AND INCOMPLETE DATA

#### 1.3.1. Per Protocol (PP) Population

Patients who have complete data collected per the protocol are the Per Protocol (PP) population.

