#### 1.3.2. Intent to Treat (ITT) Population

Patients who have met the Inclusion/Exclusion criteria and have signed the Informed Consent will be tracked. Those patients that dropped-out of the study and did not receive the investigational or control treatment will be accounted with documentation for the specific reason for not receiving the investigational or control device. Accountability for all patients that

have received the investigational or control device but have not completed all follow-up examinations will be tracked using the methods described in "Handling of Missing Data".

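### Bilateral patients supply one CRF per joint, but the named tests assume independent records and no rule says how a patient's two hips are analysed (minor)

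*Combined protocol and SAP*

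**What the plan says.** Section 1 sets the general recording rule, "Data will be recorded in a case report form on the basis of one CRF per patient", and then an exception: "For bilateral procedures, one CRF per joint must be completed". Bilateral patients are therefore expected, and the eligibility criteria in the synopsis do not exclude them.

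For analysis, Section 1 assigns chi-square and Fisher tests to qualitative variables, before versus after surgery. For quantitative variables, "The Student t test will be employed for quantitative variables for comparison between groups". No paired, clustered or mixed-model method appears anywhere.

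The counting language is about people. The synopsis heads the mean 2-year HHS as "Primary Outcome Measure for all study patients". Section 1.1 sizes the study "In order to determine Harris Hip Score with 95% confidence" and reaches a figure that "rounds to 125 subjects in GTS standard group", with the same figure for the second version. The populations are also defined by person: "Patients who have complete data collected per the protocol are the Per Protocol (PP) population" (Section 1.3.1) and "Patients who have met the Inclusion/Exclusion criteria and have signed the Informed Consent will be tracked" (Section 1.3.2).

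**The concern.** The person-based wording settles who is recruited and who belongs to each population. It does not settle what one row of the analysis is once a patient has two CRFs. A per-patient analysis would itself need a rule for two HHS values (their mean, the worse hip, the first hip), and none is given. A per-hip analysis would need a method that allows for correlation between hips of the same patient, and none is named.

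The default risk is that the CRF dataset is analysed as collected, one row per form, with methods that treat the rows as independent. Two same-version hips from one patient carry less information than two hips from different patients, so a version's mean HHS would be reported with too small a standard error. That matters mainly because the study was sized on the precision of this mean. For the t test, taking the groups to be the two stem versions (the group labels used in Section 1.1), the direction depends on whether bilateral patients have the same version on both sides or one of each.

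**Working it through.** **Plan's own figure.** Section 1.1 gives SD = 13, Z = 1.96 and a full interval width of 100 − 95 = 5. N = 4 × 13² × 1.96² / 5² = 103.88, rounded up to 104. Then 104/0.85 = 122.35, taken to 125 per version and 250 in total. This reproduces. The formula treats observations as independent. At N = 104 the width is 2 × 1.96 × 13/√104 = 5.00.

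**Assumed inputs (not in the documents).** b = share of patients with two study hips; ρ = within-patient correlation of HHS. Three scenarios: (5%, 0.3), (10%, 0.5), (20%, 0.7), each with 104 evaluable subjects per version.

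**Formulas, both hips the same version.**
- Hip records: 104(1 + b)
- Variance inflation of the all-hips mean: 1 + k, with k = 2bρ/(1 + b)
- Naive reported width: 2 × 1.96 × 13/√(hip records)
- True 95% width of the same estimate: naive width × √(1 + k)
- Actual coverage of the naive interval: 2Φ(1.96/√(1 + k)) − 1
- Mixed model with a patient random effect (ρ taken as known): effective hips = 104[(1 − b) + 2b/(1 + ρ)]; width = 2 × 1.96 × 13/√(effective hips)

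| | (5%, 0.3) | (10%, 0.5) | (20%, 0.7) |
|---|---|---|---|
| k | 0.029 | 0.091 | 0.233 |
| Hip records | 109.2 | 114.4 | 124.8 |
| Naive width | 4.88 | 4.76 | 4.56 |
| True width of that estimate | 4.95 | 4.98 | 5.07 |
| Actual coverage | 94.7% | 93.9% | 92.2% |
| Effective hips, mixed model | 106.8 | 107.5 | 107.7 |
| Mixed-model width | 4.93 | 4.92 | 4.91 |
| Mixed-model / naive width | 1.011 | 1.032 | 1.077 |

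Using one hip per patient, the width is the planned 5.00.

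**Between-version t test, true SE / reported SE (equal groups).**
- No bilateral patient has mixed versions: √(1 + k) = 1.01, 1.04, 1.11, so the reported SE is too small.
- All bilateral patients have mixed versions: √(1 − k) = 0.99, 0.95, 0.88, so the reported SE is too large.
- Half have mixed versions: the two effects cancel, ratio 1.00.

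**The case against.** The strongest reply is that a CRF rule governs data capture, not analysis, and that the plan otherwise counts patients or subjects throughout. On that reading joints would never be analysed as independent rows. This stands in part: the wording leans towards the patient, and the error arises only if the per-joint forms are used as separate rows. But leaning is not a rule, and even the patient-level reading leaves two HHS values with no instruction for combining them.

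The second reply is about size, and it largely stands. The true width of the naive estimate is 4.95 to 5.07 against a planned 5.00, so the planned precision is essentially achieved even then. What goes wrong is the reported half-width, which is too small by about 0.03, 0.11 and 0.25 HHS points in the three scenarios. The study is non-controlled, and no decision threshold is attached to the mean.

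Three stronger readings are tempting but unsupported.
- A reader might infer that the tests named in Section 1 overstate the precision of the primary outcome. None of them estimates that precision. The affected interval is only implied by the sizing in Section 1.1, and for the t test the direction of error is not fixed.
- A reader might infer that the sample size is too small. It would be affected if joints were counted towards the target, but Section 1.1 and the synopsis count subjects. With 104 evaluable subjects per version and clustering allowed for, precision stays at plan over the assumed range.
- A reader might infer that EQ-5D is double-counted. That depends on whether it is entered on both forms. CRF content is not shown, so no such claim can be made.

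**Conclusion.** The point holds as a minor one. The plan requires two records from each bilateral patient, names only independent-record tests, and does not say how the two hips are handled. If the forms are analysed as separate rows, the between-version t test has a wrong standard error in a direction that depends on the mix of versions. Any 95% interval for a version's mean 2-year HHS is too narrow where both hips carry the same version.

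Coverage of that interval would be about 94.7% to 92.2% over the assumed range, and the lower end of the range is negligible. These figures show what could happen, not what will: they rest on assumed b and ρ, on row-per-joint analysis, and on SD 13 with 104 evaluable subjects per version. No size is claimed for radiographic outcomes, EQ-5D or survivorship.

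**What to change.** Add to Section 1 of the SAP:

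> Hip-level outcomes are analysed per hip with patient as the cluster (for HHS, a mixed model with a patient random effect, which also covers a patient with one stem of each version). EQ-5D is analysed once per patient. The two CRFs of a bilateral patient are linked by a patient identifier. A sensitivity analysis uses the first-operated hip only.

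No recruitment rule is needed, because the targets are already stated in subjects.

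The cost is a short paragraph, slightly more analysis work, and a linking identifier if none exists (the documents are silent on this). No extra patients are needed. HHS intervals would be about 1%, 3% and 8% wider than the naive per-joint intervals in the three scenarios (4.93, 4.92 and 4.91 against 4.88, 4.76 and 4.56), still within the planned width of 5.0.

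### Pre- to postoperative change in qualitative variables is tested with chi-square and Fisher tests, although the values are paired and no paired method is named

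*Combined protocol and SAP*

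**What the plan says.** Section 1 (Statistical Analysis Plan) gives one rule for categorical data: "For qualitative variables, the chi-square test and a Fisher test will be performed to detect differences between preoperative and postoperative values". The only other test it names is for continuous data: "The Student t test will be employed for quantitative variables for comparison between groups". No section mentions McNemar's test, a marginal homogeneity test, GEE, a mixed model or any other paired or repeated-measures method.

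The synopsis describes the design as follows: "This is a multicenter, non-controlled, prospective study". Its Duration row says that the follow-up reviews "will be at 3 months, 1 year, 2 years, 3 years, 5 years, 7 years and 10 years", which is seven postoperative visits. The sentence on qualitative variables does not say which of them is compared with baseline.

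The outcome list ("Secondary Outcome Measures for all study patients") includes "EQ5D quality of life" and a radiographic evaluation of "stability, incidence of radiolucencies around the prosthesis and bone remodeling". On the unit of record, section 1 adds: "For bilateral procedures, one CRF per joint must be completed".

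**The concern.** With no control arm, a preoperative-to-postoperative comparison sets each patient or hip against itself. Pearson's chi-square and Fisher's exact test treat the observations as independent. The sentence does not state the table layout, and there are two possibilities:

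1. **Stacked (time by category).** The n preoperative and n postoperative values are entered as if they were 2n different patients. The pairing is ignored. With positive within-patient correlation the standard error is too large, so p-values are too large and power is lost for modest changes.
2. **Cross-table (preoperative by postoperative category).** The tests then ask whether the two values are associated, not whether the distribution has shifted. A small p-value can arise with no change, and a large one with a substantial change.

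A p-value reported for change would therefore be inefficient in the first case and would answer a different question in the second. Because seven postoperative visits are scheduled and none is named, the time point could also be chosen after the data are seen.

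**Working it through.** **Number of pairs.** Section 1.1 gives SD = 13, Z = 1.96 and X − Y = 5. The plan's own figure reproduces: 4 × 13² × 1.96² / 5² = 4 × 169 × 3.8416 / 25 = 103.88, so 104 per stem group; 104 / 0.85 = 122.35, which the plan rounds to 125. The secondary outcomes cover all patients, so the base case is 2 × 104 = 208 pairs, with 104 pairs (one stem group) as the second case.

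**Assumptions.** The documents give no category rates, no within-patient correlation (φ) and no significance level for these tests. I took a 30% preoperative rate, φ = 0.2, 0.3 and 0.5, and two-sided 5%.

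**Level of the stacked test.** With equal margins p, the variance of the paired difference in proportions is 2p(1−p)(1−φ)/n, but the stacked test uses 2p(1−p)/n. Its true level is therefore 2 × [1 − Φ(1.96/√(1−φ))], which gives 2.8%, 1.9% and 0.6% for φ = 0.2, 0.3 and 0.5.

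**Simulation.** Paired binary data, 200,000 replicates, no continuity correction. Entries are rejection rates at φ = 0.2 / 0.3 / 0.5.

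| True rates | Pairs | Stacked chi-square | McNemar |
|---|---|---|---|
| 30% to 30% | 208 | 2.8 / 2.0 / 0.6% | 5.0 / 5.0 / 5.0% |
| 30% to 30% | 104 | 2.9 / 2.0 / 0.6% | 5.1 / 5.2 / 5.3% |
| 30% to 42% | 208 | 75 / 76 / 80% | 82 / 86 / 95% |
| 30% to 42% | 104 | 44 / 43 / 42% | 52 / 58 / 74% |
| 30% to 50% | 208 | all above 99% | all above 99% |
| 30% to 50% | 104 | 87 / 89 / 93% | 91 / 94 / 99% |
| 30% to 60% | both | all above 99% | all above 99% |

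The stacked Fisher test (40,000 replicates) is more conservative still: with no change it rejects 2.1 / 1.4 / 0.4% at 208 pairs and 1.9 / 1.2 / 0.4% at 104. At φ = 0 nothing is lost: for 30% to 42%, stacked chi-square and McNemar have 44% and 43% power at 104 pairs, and 72% each at 208.

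**Cross-table chi-square.** With no change (30% to 30%) it rejects 81 / 99 / 100% at 208 pairs and 53 / 85 / 99.9% at 104. With a real change from 30% to 42%, or to 60%, and φ = 0, it rejects about 5% at either size.

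**Worked tables, n = 104** (cells: yes/yes, yes/no, no/yes, no/no):

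- (40, 4, 14, 46): 44/104 = 42% before, 54/104 = 52% after. Stacked chi-square p = 0.165, stacked Fisher p = 0.211, exact McNemar p = 0.031.
- (40, 12, 12, 40): 50% before and after. Cross-table chi-square = 104 × (40×40 − 12×12)² / 52⁴ = 30.2, p = 4 × 10⁻⁸; McNemar p = 1.0.
- (13, 39, 13, 39): 50% before, 25% after. Cross-table numerator 13×39 − 39×13 = 0, so p = 1.0; exact McNemar p = 0.0004.

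**More than two categories.** For an assumed 3×3 table with equal margins (34/34/32%) but asymmetric cells, Stuart-Maxwell holds its level (5.1% at both sizes). Stacked chi-square rejects 0.4% at 104 pairs and 0.5% at 208. Bowker's symmetry test rejects 97% and over 99.9%, so it is no substitute for a test of marginal change.

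**Bilateral patients.** If two hips of one patient are counted as independent, the design effect is 1 + ICC × 2f/(1+f), where f is the share of patients with two hips and ICC is the between-hip correlation of the pre-post change. Assume f = 0.20 and φ = 0.2:

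- ICC = 0.8: 1 + 0.8 × 0.4/1.2 = 1.267. The stacked variance ratio is 1.267 × 0.8 = 1.013, level 5.2%; McNemar's level is 8.2%.
- ICC = 1 (a patient-level answer entered twice): 1.333. The stacked level is 5.8% and McNemar's 9.0%.

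McNemar's test therefore also needs a rule for bilateral cases.

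**The case against.** The core cannot be disputed, but several limits can be pressed.

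- **Reach.** The primary outcome is a mean score. Radiolucency around the prosthesis, implant stability, revision and survivorship have no preoperative value. EQ5D falls under the sentence only if its items are analysed as categories; an index would be quantitative. No listed outcome is shown to be affected, and no success criterion rests on such a test. This stands, and it limits the severity.
- **Layout.** A sentence about differences between two times reads more naturally as the stacked layout, and the most striking figures come from the cross-table. That is fair, but nothing in the plan excludes the cross-table, and the stacked layout is also wrong.
- **Size of the loss.** Too few rejections do not create false claims. The loss vanishes for large changes and at zero correlation. Against exact McNemar at φ = 0.2, the gain for 30% to 42% is small: 45.6% versus 43.6% at 104 pairs, and 78.1% versus 74.7% at 208. At negative correlation the stacked test is anti-conservative: 7.6% at φ = −0.3, with 50% margins and 104 pairs. All of this stands. It shows that the direction and size of the error depend on a correlation nobody has stated.
- **Bilateral figures.** A 20% share with correlation of 0.8 or more is a demanding case. With 10% and 0.5 the design effect is 1 + 0.5 × 0.2/1.1 = 1.091, and the stacked level at φ = 0.2 is about 3.6%, still conservative. This stands; the figures illustrate the need for a rule and do not estimate the effect.
- **Scope.** The visit and the bilateral rule go beyond the choice of test. They do, but a paired test cannot be specified without its time point and its unit.
- **Ordered categories.** Stuart-Maxwell ignores the ordering of EQ5D levels. This stands and is taken up in the fix.

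**Conclusion.** The concern holds. As written, the plan assigns tests for independent samples to paired data and names no paired alternative. This is a wrong rule, not merely a missing detail.

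Under the stacked layout with positive within-patient correlation of 0.2 to 0.5, the level falls from 5% to between 2.8% and 0.6%, and power for a modest change drops by roughly 7 to 15 percentage points at 208 pairs (82 − 75 and 95 − 80). For large changes the loss is negligible. Under the cross-table layout the result says nothing about change and can point in the opposite direction.

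These sizes rest on assumed rates, correlations and a 5% level. The effect is confined to qualitative variables measured both before and after surgery, which the documents do not list. The primary outcome and the figures 104, 122 and 125 do not change. The sentence should be corrected, but it does not threaten the study's main result.

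**What to change.** Replace the sentence on qualitative variables in section 1 with wording such as:

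> Change between preoperative and postoperative categories at a prespecified postoperative visit is tested with McNemar's test (binary; exact if discordant pairs are few) or a marginal homogeneity test such as Stuart-Maxwell (more than two categories), with the paired difference and 95% CI. Chi-square or Fisher tests are used only for comparisons between stem groups. Outcomes that exist only after surgery are reported as incidence with 95% CI. If both hips of a patient are analysed, one hip per patient is chosen by a rule fixed in advance or a patient-clustered method is used; patient-level measures such as EQ5D are counted once per patient.

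The sponsor should also list the qualitative variables to which this applies. If EQ5D items are to be tested as ordered levels, a paired method that uses the order should be named for them.

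The cost is SAP wording. The paired tests use the same values that the current sentence already presumes, the sample size does not move, and the bilateral rule needs only a patient identifier linking the two joint CRFs.

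### If the undefined groups in the planned t test are the two stem versions, the comparison is neither randomised nor adjusted, so a difference in case mix could be read as a difference between stems

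*Combined protocol and SAP*

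**What the plan says.** The synopsis describes the design as "This is a multicenter, non-controlled, prospective study" and the population as "250 subjects suitable for GTS femoral stem (standard and lateralized) can be included". The primary outcome is "Mean Harris Hip Score (HHS) at 2 year postoperative", set for all study patients.

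The eligibility section of the synopsis has one list of indications for both stem versions. It has six entries: osteoarthritis, inflammatory hip disease, femoral neck fracture, avascular necrosis, congenital dysplasia, and "Sequelae from previous operations on the hip, osteotomies, etc".

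Section 1.1 calculates 125 subjects for the standard stem and then adds: "The same calculation applied to GTS varized group". Section 1.2, on randomisation, says only that it does not apply. No section says how a patient comes to receive one version or the other.

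Section 1 gives the test for quantitative variables: "The Student t test will be employed for quantitative variables for comparison between groups". It names no covariate, stratification or weighting. The sensitivity analysis in Section 1.3.3 concerns missing data only, and no section plans a baseline comparison of the two versions.

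**The concern.** A two-sample t test isolates the effect of the stem version only if the two sets of patients are otherwise comparable. Nothing in this plan makes them so. The version is not assigned at random, no selection rule is stated, and patients come from five centres with six indications. If indication, age or centre is related both to the version received and to the 2-year HHS, the unadjusted difference mixes that relation with any stem effect.

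A link between indication and version is plausible. The version names suggest a difference in geometry, and the entry list includes dysplasia and previous osteotomy, which can alter hip anatomy. The concern does not depend on that route alone, because a preference by centre or by age would act in the same way.

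What is at stake is the reading of any comparison between versions in the study reports. A difference could reflect who received which stem, and a true difference could be hidden for the same reason.

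**Working it through.** **1. The plan's own sample size (Section 1.1).** Inputs: SD 13, Z = 1.96, X − Y = 5.

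N = 4 × 13² × 1.96² / 5² = 4 × 169 × 3.8416 / 25 = 103.88, so 104.
104 / 0.85 = 122.35; the plan gives 122 and rounds to 125. Two groups: 2 × 125 = 250.

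The plan's figures reproduce. They set the precision of each version's mean: half-width 1.96 × 13 / √104 = 2.50 points. They are not a sizing for a comparison between versions.

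**2. Precision of the comparison with the same inputs.**

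SE of the difference = 13 × √(2/104) = 1.803 points.
95% half-width = 1.96 × 1.803 = 3.53 points.

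**3. Bias from case mix.** Suppose the stems are equally good and the groups differ only in the share of an indication with a lower 2-year HHS. Then

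bias = (difference in share) × (HHS gap for that indication).

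The chance that the nominal two-sided 5% test rejects is approximately

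P(Z > 1.96 − bias/SE) + P(Z < −1.96 − bias/SE).

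The shares and gaps below are assumptions, because the documents give neither.

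| Difference in share | HHS gap (points) | Bias (points) | Bias/SE | Rejection rate |
|---|---|---|---|---|
| 0 | any | 0 | 0 | 5.0% |
| 10 percentage points | 5 | 0.5 | 0.28 | 5.9% |
| 10 percentage points | 10 | 1.0 | 0.55 | 8.6% |
| 20 percentage points | 10 | 2.0 | 1.11 | 19.9% |
| 30 percentage points | 10 | 3.0 | 1.66 | 38.4% |

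For the 2.0-point row: P(Z > 0.85) + P(Z < −3.07) = 0.198 + 0.001, about 0.20.

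The table also assumes 104 evaluable in each group, a common SD of 13, and independent observations.

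**The case against.** The strongest reply is that Section 1 never says the groups are stem versions. The sentence before the t test concerns change from before to after surgery, and the t-test sentence may be a loose parallel to it for quantitative variables. This stands as a limit: reading the groups as stem versions is an inference. It is the best-supported one, because Section 1.1 names and sizes exactly two groups and no others appear. If something else was meant, the sentence still needs correcting, since it leaves the contrast undefined.

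A second reply is that no objective depends on the comparison. The study is non-controlled, its primary outcome is a descriptive mean, and each version is sized for precision, with no between-version hypothesis, margin or power. This also stands. A reader might infer that the primary result is biased, or that the study would wrongly flag or clear one version. The documents support neither. Case mix leaves each descriptive mean a valid description of the patients studied, and no decision rule is tied to the t test.

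A third reply is that the mechanism and its size are not in the documents. That is correct. They do not say how the version is chosen, how indications divide between versions, or that HHS differs by indication. A reader might infer that case-mix differences will be taken for stem effects. The text supports only that they could be, if the mix differs and the indications differ in outcome. In the mildest non-zero case shown, the rejection rate barely moves from 5%.

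None of this makes the unadjusted test a suitable way to compare two non-randomised versions.

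**Conclusion.** The concern holds in conditional form. If the groups are the stem versions, the planned t test cannot separate a stem effect from differences in indication, age or centre, and nothing else in the plan does so. Direction and size are unknown. Over the assumed range of 0.5 to 3.0 points of bias, the false-positive rate runs from about 6% to 38% against a nominal 5%, and it stays at 5% without imbalance. These rates use the plan's SD and evaluable number; the imbalances and HHS gaps are illustrative. The descriptive primary mean HHS is untouched. This is worth correcting in the SAP but does not undermine the study's main aim.

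**What to change.** In Section 1:

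- State that the groups are the standard and the lateralized (varized) stem, and use one name for the latter throughout.
- Replace the t test for 2-year HHS with a linear model of HHS on stem version, adjusted for indication, age and centre.
- Where numbers allow, keep osteoarthritis, fracture, and dysplasia or previous hip operation as separate categories. A simple split of osteoarthritis against the rest would pool the diagnoses most likely to bear on geometry with unrelated ones, and could leave much of the confounding in place.
- Add preoperative HHS only in a supporting analysis limited to non-fracture hips. In the main model, hips without a preoperative score would be dropped by complete-case handling, and fracture hips are the ones at risk.
- Tabulate indication, age and centre by stem version, and label the comparison observational.

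If no inferential comparison is intended, the alternative is to say so, remove the test, and report each version descriptively with the same table.

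The cost is SAP wording and one regression in SPSS, using data known at enrolment. Recruitment, treatment and follow-up do not change. With four indication categories and five centres, adjustment uses 3 + 1 + 4 = 8 degrees of freedom out of about 208 evaluable hips (2 × 104). Precision would fall further if version is closely tied to centre or indication. Unmeasured confounding remains, which is why the observational label is needed.

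### The comparison between stem versions uses an unadjusted t test although version is not randomised and patients come from five centres; centre should be in the model

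*Combined protocol and SAP*

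**What the plan says.** The synopsis describes a multicentre study without a control arm: "Study will be conducted in 5 centers across Europe (Germany, Italy, Spain, France". The primary outcome is the mean HHS two years after surgery. Section 1.2 marks randomisation as not applicable.

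Section 1 gives one method for quantitative outcomes: "The Student t test will be employed for quantitative variables for comparison between groups". It does not define the groups. The groups that the document does set up are the two stem versions in section 1.1, where the standard group is sized first and then "The same calculation applied to GTS varized group". The synopsis calls the second version lateralized.

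Section 1.1 sizes each group for the precision of one mean: "In order to determine Harris Hip Score with 95% confidence: then Z = 1.96", "If HHS is between 95 to 100: then X=100 and Y=95" and "Estimate standard deviation of HHS at follow-up = 13". The formula has no centre term. Neither section 1 nor its subsections mention centre effects, stratification or adjustment for centre, and nothing says how the two versions are to be spread over the centres.

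**The concern.** Stem version is chosen, not allocated. Nothing in the plan prevents one centre from using mostly the standard stem and another mostly the lateralized one. HHS may also differ between centres for reasons unrelated to the stem; the documents do not say what those might be, but five centres in four countries make it plausible.

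If both happen, the two version means are averages over different mixtures of centres. Their raw difference then contains a centre difference, and the t test attributes it to the stem. A reader of the final report could take a difference between hospitals for a difference between implants, or miss a real implant difference that the hospitals mask. This does not depend on viewing the five centres as a sample of others: for these five centres it is ordinary confounding.

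**Working it through.** **The plan's own figure.** From section 1.1: SD 13, Z 1.96, X − Y = 5.

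- N = 4 × 13² × 1.96² / 5² = 103.88, rounded up to 104. Reproduced.
- Half-width at N = 104: 1.96 × 13 / √104 = 2.50. The factor 4 therefore makes the 5 points the full width of the interval, plus or minus 2.5.
- 104 / 0.85 = 122.4, which the plan writes as 122 and rounds to 125 per group. The difference is immaterial.

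**The version comparison.** Inputs from the documents: 104 evaluable patients per version, SD 13, five centres. Assumed, because the documents do not give them: ICCs of 0.02, 0.05 and 0.10 (between-centre SD 13 × √ICC = 1.84, 2.91 and 4.11 points), and the split of versions over centres.

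Let a and b be the numbers of standard and lateralized patients in each centre. With total variance held at 13², the true variance of the difference in means, in units of 13², is

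2(1 − ICC)/104 + ICC × D, where D = Σ(a − b)² / 104².

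The t test works with roughly 2/104. With R the ratio of true to assumed variance, the type I error is 2 × [1 − Φ(1.96/√R)].

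*Uneven split*, 35/30/20/12/7 against 7/12/20/30/35: the differences are 28, 18, 0, −18, −28, so D = 2216/10816 = 0.2049. At ICC 0.05 the true variance is 0.01827 + 0.01024 = 0.02851, against 2/104 = 0.01923. Then R = 1.483, √R = 1.218, and the type I error is 10.7%.

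*Balanced within centres*: D = 0 and R = 1 − ICC, so the test is conservative.

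| Split of versions | Method | ICC 0.02 | ICC 0.05 | ICC 0.10 |
|---|---|---|---|---|
| Balanced within centres | formula | 4.8% | 4.4% | 3.9% |
| | simulation | 4.6% | 4.6% | 4.0% |
| Uneven, as above | formula | 7.3% | 10.7% | 16.2% |
| | simulation | 7.1% | 11.1% | 16.5% |
| Versions in different centres (two against three) | simulation | 15% | 27% | 40% |

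The simulations used 20,000 runs per cell, so they carry a Monte Carlo error of a few tenths of a point.

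Seen as bias for these five centres, the raw difference in the uneven split is shifted by Σ(a − b)/104 × (centre effect). At ICC 0.05 that shift has a standard deviation of 13 × √(0.05 × 0.2049) = 1.32 points, against a nominal standard error of 13 × √(2/104) = 1.80.

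**What adjustment costs.** With centre as a fixed factor, the standard error of the version effect is 13 × √[(1 − ICC) / Σ ab/(a + b)].

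- Balanced: the sum is 52, and at ICC 0.05 the standard error is 1.76, slightly below the nominal 1.80.
- Uneven: the sum is 5.83 + 8.57 + 10 + 8.57 + 5.83 = 38.81, and at ICC 0.05 the standard error is 2.03.
- No centre using both versions: the sum is 0, and version cannot be separated from centre.

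**The case against.** The strongest reply is that this is a descriptive post-market study with no hypothesis, margin or decision rule. No comparison of the two versions is listed among the aims or outcomes, and section 1 does not say which groups the t test compares. Nor do the documents show that version use differs by centre; if it does not, the t test is safe and even slightly conservative. All of this stands. It limits the point to a cheap improvement. It does not remove the point, because the plan does commit to a test between groups, the stem versions are the only groups it sets up, and nothing in it secures balance.

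A reader might also infer that any variation between centres makes the 95% interval for the mean HHS too narrow, so that 104 is too few. The documents do not support that. For the mean in these five centres the pooled interval is not too narrow. It becomes so only if the centres are treated as a random sample of a wider population, which the plan does not claim. Under that reading, with equal centres of 104/5 = 20.8 patients per version, the design effect is 1 + 19.8 × ICC. The full width would be 5.0 × √1.396 = 5.9 at ICC 0.02 and 5.0 × √1.99 = 7.05 at ICC 0.05. These are illustrations under assumed inputs, not errors in the stated figure, and a fixed centre factor would not produce those widths.

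The per-joint case report form for bilateral cases raises a separate question of correlation within patients. Section 1.1 counts subjects, and the figures here do too.

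**Conclusion.** The concern holds for the version comparison. An unadjusted t test between stem versions, in a five-centre study without randomisation, leaves centre uncontrolled as a confounder. If the version mix is uneven in the way illustrated, a nominal 5% test has a type I error of about 7% at ICC 0.02, 11% at 0.05 and 16 to 17% at 0.10. If the versions are balanced within centres it is about 4 to 5%. The result rests on assumed ICCs and an assumed split, and on reading the groups in section 1 as the two stem versions.

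It does not extend to the sample size: 104 and its 5-point width are correct for what they describe. Section 1.1 lacks only a statement of scope. This is a worthwhile improvement at small cost, not a fault that undermines the study.

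**What to change.** - **Section 1.** State that the groups are the two stem versions. Replace the t test between them with a linear model of 2-year HHS on version, with centre as a fixed factor. Treat other quantitative outcomes compared between versions in the same way.
- **Reporting.** Give the number of patients and the mean HHS for each version in each centre. A centre that uses only one version adds nothing to the adjusted comparison; if no centre uses both, say that the versions cannot be compared free of centre and report them descriptively.
- **Section 1.1.** Add that the 5-point full width (plus or minus 2.5 at 104 patients) refers to these five centres and makes no allowance for variation between centres. If results are to be generalised further, show the 5.9 and 7.05 widths as illustrations, with their assumptions.

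The cost is SAP wording and 4 degrees of freedom (206 to 202 with 208 patients), with no new data. Precision falls if version and centre are strongly confounded: in the uneven example at ICC 0.05 the standard error is 2.03 points rather than the nominal 1.80.
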